6.2. Summaries and Analyses for PK Endpoints

Unless otherwise specified, PK summaries will use the Pharmacokinetic Set.

Plasma concentrations of Etrasimod will be assessed from PK samples collected prior to dosing and 4 hours (± 15 minutes) postdose (after 12-lead ECG) on Week 0/Day 1. Additionally, PK samples will be collected prior to dosing (trough) at Weeks 2, 4, 8, 12, 16, 20, 24, 32, 40, 48, and 52, and for PK samples collected at the 2-Week and 4-Week Follow-Up visits for participants not enrolled into any extension study.

Concentrations below the limit of quantitation (BLQ) will be assigned a numerical value of zero for the calculation of descriptive statistics. For geometric mean and geometric % coefficient of variation [CV], the zero values will be excluded.

Individual participant etrasimod plasma concentrations (and etrasimod metabolite concentrations, if applicable) will be presented in the data listings, including participant ID, treatment received, nominal timepoint, actual blood collection date/time, concentration, and time since last dose and also summarized using descriptive statistics (n, mean, SD, % CV, geometric mean, geometric % CV, median, minimum, and maximum) by nominal timepoint.

All participants are expected to achieve steady-state plasma concentration by Week 2. For each participant, the average steady-state trough (predose) plasma concentration based on Week 2 to Week 52 trough concentrations (C_{trough,ss},W2-W52) per participant will also be calculated and presented in a data listing and summarized using descriptive statistics.

Mean (\pm SD) etrasimod concentration versus nominal time (Weeks 0 to 52) will be plotted on a linear scale.

The pharmacokineticist will determine the strategy for dealing with data affected by protocol deviations or events which may impact the quality of PK concentration data on a case-by-case basis with input from the study physician and clinical pharmacologist, as needed. Examples for protocol deviations or events include, but may not be limited to, vomiting on the day prior to trough sample collection, sample processing errors that lead to inaccurate bioanalytical results, and/or inaccurate dosing prior to PK sampling.

The plasma concentrations over time will be used in a population PK analysis, which will be described in a separate analysis plan.

6.3. Safety Summaries and Analyses

All outputs for safety outcomes will be based on the Safety Set.

6.3.1. Adverse Events

6.3.1.1. All TEAEs

All TEAEs will be summarized by SOC and PT. This summary table and all other TEAE summaries by SOC and PT will be presented by descending frequency in the etrasimod group.

All AEs, regardless of treatment-emergent status, will be included in an AE listing. Additionally, a listing of other AE details as collected on the CRF will be presented. Exposure-adjusted incidence rate (EAIR) of TEAEs will be summarized by SOC and PT. Exposure is defined as the sum of either time (year) from first dose to the onset of first such event for those who experienced this AE, or time (year) from first dose to last participation for those who did not experience this AE. The EAIR is calculated as the number of participants with the AE divided by the total exposure in participant-years.

Severity

All TEAEs will be summarized by SOC, PT, and maximum severity, with SOC and PT presented by descending frequency. If a participant reports a TEAE more than once within a SOC/PT, the AE with the worst-case severity will be used in this summary.

Relationship to Study Treatment

All related TEAEs will be summarized by SOC, PT, and maximum severity, with SOC and PT presented by descending frequency. If a participant reports a TEAE more than once within a SOC/PT, the AE with the worst-case severity will be used in this summary. A "related TEAE" for the purpose of this summary is defined as a TEAE with relationship to study treatment of "probably related" or "related".

6.3.1.2. TEAEs Leading to Discontinuation of Study Treatment and TEAEs Leading to Interruption of Study Treatment

All TEAEs leading to discontinuation of study treatment will be summarized by SOC and PT. TEAEs leading to interruption of study treatment will be summarized by SOC and PT as well.

6.3.1.3. Serious and Non-Serious TEAEs

All serious TEAEs will be summarized by SOC and PT. If the seriousness is missing, the AE will be considered as "Serious" for summary tabulation purpose only. All nonserious TEAEs will be summarized by SOC and PT.

6.3.1.4. TEAEs of Special Interest

TEAEs of special interest will be summarized by category, subcategory, and PT by descending frequency by treatment group.

For each category, subcategory, and PT, model-based analysis will be performed to compare treatment effect between etrasimod and placebo. An extended Cox regression model will be used to handle recurring AEs (Cao 2011, Section 8 References). The stratification variables, naïve to biologic or JAK inhibitor therapy status at study entry (Yes or No) and Baseline corticosteroid use (Yes or No), will be included in the model. A participant with K events contributes (K+1) observations to the input data set; here K might be 0. The k-th observation of the participant identifies the time interval from the start date of the (k-1)-th event, or time 0 (if k = 1), to the start date of the kth event, k = 1, ..., K. The (K+1)-th observation represents the time interval from the K-th event to the date of censorship, ie, the date of last dose or date of last study visit up to Week 52, whichever is later. Hazard ratios (Etrasimod group vs placebo group), 95% CIs, and 2-sided p-values for treatment effect comparison will be presented.

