6.3.1.5. Overall Summary of Adverse Events

In addition to the summaries above, an overview of TEAEs will be summarized by number and frequency of participants and by number of AEs:

- Any TEAE
- Any related TEAE*
- Any serious TEAEs
- Any related serious TEAEs*
- TEAEs leading to death
 - Liver-related TEAEs leading to death
- TEAEs leading to study treatment discontinuation
 - Related TEAEs leading to study treatment discontinuation*
 - Liver-related TEAEs leading to study treatment discontinuation
- TEAEs leading to study treatment interruption
 - Related TEAEs leading to study treatment interruption*
- TEAEs by maximum severity
- Related TEAEs by maximum severity*
- TEAEs by relationship to study treatment

^{* &}quot;Related TEAEs" refers to TEAEs related or probably related to study treatment or are missing relationship.

Comparative analyses will be performed for the following:

- TEAEs leading to Deaths
- Severe TEAEs (CTCAE grade ≥ 3)
- Serious TEAEs
- TEAEs leading to study treatment discontinuation.
- TEAEs of special interest
- Treatment-emergent Serious infections
- Treatment-emergent Opportunistic infections (Narrow)
- Treatment-emergent Malignancies

Risk differences between etrasimod and placebo along with 95% CIs using the Wilson's score method will be presented. Differences between "Exposure-Adjusted Incidence Rates" (EAIR) comparing treatment to placebo along with 95% CIs based on large-sample approximation assuming Poisson standard errors for the estimated incidence rates as described in Liu et al. will be presented as well.

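### The special-interest event Cox model has no rule for an arm with no events and names neither test nor variance, so for sparse terms the hazard ratio does not exist and the printed p-value depends on software defaults

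*SAP*

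**What the plan says.** SAP 6.3.1.4 starts with counts: "TEAEs of special interest will be summarized by category, subcategory, and PT by descending frequency by treatment group". It then adds inference at all three levels: "For each category, subcategory, and PT, model-based analysis will be performed to compare treatment effect between etrasimod and placebo". The method is given as "An extended Cox regression model will be used to handle recurring AEs", with the two randomisation factors in the model, and the data layout as "A participant with K events contributes (K+1) observations to the input data set; here K might be 0". The output is fixed: "Hazard ratios (Etrasimod group vs placebo group), 95% CIs, and 2-sided p-values for treatment effect comparison will be presented".

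The section does not give a minimum event count, a display rule for an arm with no events, or a penalised or exact fallback. It does not say whether the p-value is Wald, score or likelihood-ratio, or whether the variance is model-based or robust to repeated events within a participant. The one sparse-data rule we found, in SAP 6.4, withholds inference for efficacy subgroups below 5% of participants. It does not reach this analysis.

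SAP 6.3.1.5 includes special-interest events in its list of comparative analyses: "Risk differences between etrasimod and placebo along with 95% CIs using the Wilson's score method will be presented". It adds exposure-adjusted incidence rate (EAIR) differences with "95% CIs based on large-sample approximation assuming Poisson standard errors for the estimated incidence rates". It does not say whether these apply overall, by category or by preferred term.

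**The concern.** The special-interest list in SAP 3.2.2.1 contains events likely to be rare, such as macular edema, AV conduction delay, opportunistic infections and malignancies, and the model is run down to single preferred terms. Placebo is the smaller arm. Many of these terms can therefore be expected to have events in one arm only.

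The Cox partial likelihood then rises without limit as the log hazard ratio moves away from zero. There is no maximum, and software stops at an arbitrary large value. What is printed beside it depends on the variance and test the program uses by default, which the SAP leaves open. At stake is a safety table with numbers that look like inference but carry none, and that could err in either direction.

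**Working it through.** The documents give no figure for this model, so there is none to reproduce.

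**Inputs.** Planned arms are 150 etrasimod and 75 placebo (SAP 2.3). Assumed, because not in the documents: event incidence r of 0.5%, 1% or 2%, equal in both arms; about 70% of participants followed to Week 52; stratum prevalences of 70% and 30%; 0.8 years of exposure per participant; one event per affected participant.

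**1. How often exactly one arm is empty.** Let a = (1−r)^150 and b = (1−r)^75. The chance, given at least one event, is (a + b − 2ab)/(1 − ab).

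| r | a | b | ab | Calculation | Result |
|---|---|---|---|---|---|
| 0.5% | 0.471 | 0.687 | 0.324 | 0.511/0.676 | 76% |
| 1% | 0.221 | 0.471 | 0.104 | 0.484/0.896 | 54% |
| 2% | 0.048 | 0.220 | 0.011 | 0.247/0.989 | 25% |

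These count either arm being empty.

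**2. What the fit prints with k etrasimod participants affected and none on placebo.** An Andersen–Gill Cox model was fitted to simulated counting-process data by Newton–Raphson; the model-based and robust Wald results were checked in standard survival software at 5, 10 and 20 v 0. The log hazard ratio stops near 19.7, a hazard ratio of about 3.5×10^8.

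| k v 0 | Model-based Wald p | Robust Wald p | Likelihood-ratio p | Score p | Fisher p |
|---|---|---|---|---|---|
| 3 | 0.999 | about 10^−249 | 0.12 | 0.22 | 0.55 |
| 5 | 0.999 | prints 0 | 0.043 | 0.11 | 0.17 |
| 8 | 0.998 | prints 0 | 0.0099 | 0.042 | 0.054 |
| 10 | 0.998 | prints 0 | 0.0065 | 0.034 | 0.033 |
| 20 | 0.997 | prints 0 | 0.0001 | 0.0015 | 0.0003 |

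The model-based SE is about 12,000 at k = 5 and 5,800 at k = 20, with a CI from 0 to infinity. The robust SE is about 0.46 at k = 5, with a CI of about 1.5×10^8 to 9.0×10^8. Both are artefacts of where the iteration stopped.

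**3. The risk difference of SAP 6.3.1.5.** Wilson's method is taken in Newcombe's form for a difference. At 10 v 0, the Wilson limits are 3.66% and 11.84% for 10/150, and the upper limit for 0/75 is 4.87%.
- Difference: 10/150 = 6.67%.
- Lower limit: 6.67 − √((6.67−3.66)² + 4.87²) = 0.9%.
- Upper limit: 6.67 + (11.84−6.67) = 11.8%.

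Other splits: 5 v 0 gives 3.3% (−1.9 to 7.6); 8 v 0 gives 5.3% (−0.2 to 10.2); 20 v 0 gives 13.3% (6.7 to 19.7). The interval stays finite and behaves sensibly.

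**4. The EAIR difference of SAP 6.3.1.5.** At 5 v 0, exposure is 150 × 0.8 = 120 years on etrasimod. The difference is 5/120 = 0.042 with SE √5/120 = 0.0186, because the placebo arm contributes zero variance. The CI is 0.042 ± 1.96 × 0.0186 = 0.005 to 0.078. It excludes zero although Fisher p = 0.17, so this comparison also fails with an empty arm.

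**5. A Firth-penalised fit.** With constant 2:1 risk sets and p = 2e^β/(2e^β + 1), maximise k·log p + ½·log(k·p(1−p)). Setting the derivative to zero gives p = (k+½)/(k+1), so HR = k + ½. Profile-likelihood results: 5 v 0, HR 5.5 (0.62 to 722), p = 0.15; 8 v 0, 8.5 (1.06 to 1099), p = 0.042; 10 v 0, 10.5 (1.35 to 1350), p = 0.019; 15 v 0, 15.5 (2.09 to 1979), p = 0.002.

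**The case against.** A reader might infer that the plan would report an all-etrasimod imbalance as no difference. The documents do not support that.

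- A p-value near 1 follows only from a model-based Wald test, and SAP 6.3.1.4 names no test. A robust variance gives the opposite error; likelihood-ratio and score p-values do not go to 1.
- The same section tabulates counts by arm, so 10 v 0 would sit beside a hazard ratio near 10^8. That looks like a failed fit, not like equality.
- SAP 6.3.1.5 lists special-interest events for risk differences, and that interval excludes zero at 10 v 0. Conduction abnormalities and retinal thickness also have their own summaries (SAP 6.3.2.2, 6.3.2.3 and 6.3.2.6).
- Up to 8 v 0, Fisher's test is also non-significant; it first falls below 0.05 at 9 v 0 (p = 0.031).
- Most empty-arm terms hold very few events: at 0.5% and 1% incidence, 94% and 80% of them have at most two. With equal incidence, 9 or more v 0 has probability 6×10^−8, 10^−5 and 0.0007 at the three rates.
- Type I error control covers efficacy only, and no safety rule in the SAP uses this p-value.

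All of this stands and limits the harm. It does not make the planned output valid. Nothing in SAP 6.3.1.4 lets the hazard ratio be withheld, and SAP 6.3.1.5 neither states its level nor says that it replaces an inestimable ratio. The small counts cut both ways: with a robust variance, 3 v 0 would print as overwhelming evidence.

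**Conclusion.** Wrong as written, with limited consequences. Following SAP 6.3.1.4 literally prints a hazard ratio, CI and p-value that have no meaning whenever one arm is empty. At 10 v 0 the unspecified choice yields p of 0.998, 0.034, 0.0065 or about 0.

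The divergence is a property of the model and needs no assumption. Its frequency (76%, 54%, 25%) rests on the planned arm sizes and on assumed equal incidences. The printed SEs and p-values depend on simulated follow-up and on where the software stops, but the direction of each failure does not. The documents do not support a claim that a safety signal would be hidden: the p-value can err either way, and counts and risk differences remain visible.

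**What to change.** In SAP 6.3.1.4:

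- Fit the extended Cox model only for terms with events in both arms, and state a participant-clustered variance for recurrent events.
- For a term with an empty arm, show the hazard ratio as not estimable and report the Wilson-score risk difference of SAP 6.3.1.5 at that same level (category, subcategory or preferred term). Do not rely on the EAIR difference there, because its Poisson variance is zero in the empty arm.
- Alternatively, for those terms, fit a Firth-penalised Cox model to time to first event with profile-likelihood CI and p-value. Using the first event avoids within-participant correlation, which the penalty does not address.

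The cost is a few sentences in the SAP and slightly more programming, with no new data. Intervals for sparse terms will be very wide, as the Firth interval of 0.62 to 722 at 5 v 0 shows.

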6.3.1.5. Overall Summary of Adverse Events

In addition to the summaries above, an overview of TEAEs will be summarized by number and frequency of participants and by number of AEs:

- Any TEAE
- Any related TEAE*
- Any serious TEAEs
- Any related serious TEAEs*
- TEAEs leading to death
 - Liver-related TEAEs leading to death
- TEAEs leading to study treatment discontinuation
 - Related TEAEs leading to study treatment discontinuation*
 - Liver-related TEAEs leading to study treatment discontinuation
- TEAEs leading to study treatment interruption
 - Related TEAEs leading to study treatment interruption*
- TEAEs by maximum severity
- Related TEAEs by maximum severity*
- TEAEs by relationship to study treatment

^{* &}quot;Related TEAEs" refers to TEAEs related or probably related to study treatment or are missing relationship.

Comparative analyses will be performed for the following:

- TEAEs leading to Deaths
- Severe TEAEs (CTCAE grade ≥ 3)
- Serious TEAEs
- TEAEs leading to study treatment discontinuation.
- TEAEs of special interest
- Treatment-emergent Serious infections
- Treatment-emergent Opportunistic infections (Narrow)
- Treatment-emergent Malignancies

Risk differences between etrasimod and placebo along with 95% CIs using the Wilson's score method will be presented. Differences between "Exposure-Adjusted Incidence Rates" (EAIR) comparing treatment to placebo along with 95% CIs based on large-sample approximation assuming Poisson standard errors for the estimated incidence rates as described in Liu et al. will be presented as well.

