9.9.9.1.6. Relationship

The Investigator (or designee) will make a determination of the relationship of the AE to the study drug using a 4-category system according to the following guidelines:

Not Related: The AE is definitely caused by the subject's clinical state or the study

procedure/conditions.

Unlikely Related: The temporal association between the AE and the drug is such that the

drug is not likely to have any reasonable association with the AE.

Probably Related: The AE follows a reasonable temporal sequence from administration of

the drug and cannot be reasonably explained by the known

characteristics of the subject's clinical state, environmental, or toxic

factors, or other modes of therapy administered to the subject.

Related: The AE follows a reasonable temporal sequence from administration of

the drug, abates upon discontinuation of the drug, follows a known or hypothesized cause-effect relationship, and (if appropriate) reappears

when the drug is reintroduced.

The Investigator will use clinical judgement to determine the relationship. Alternative causes, such as underlying disease(s), concomitant therapy, and other risk factors, as well as the temporal relationship of the event to the study treatment administration should be considered and investigated. The Investigator should consult the IB and the Product Information of marketed products within the drug class, when applicable. For each adverse event/SAE, the Investigator must document in the medical notes that he/she has reviewed the adverse event/SAE and has provided an assessment of causality. There may be situations in which an SAE has occurred and the Investigator has minimal information to include in the initial report to the Sponsor; however,

it is very important that the Investigator always make an initial assessment of causality for every event before the initial transmission of the SAE to the Sponsor. The Investigator may change his/her opinion of causality based on subsequent receipt of information and send an SAE follow-up report with the updated causality assessment. The causality assessment is one of the criteria used when determining regulatory reporting requirements.

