3.2.2. Safety Endpoint(s)

3.2.2.1. Adverse Event

AEs will be coded using MedDRA (v27.0). The version used to code AEs will be displayed in the analyses. Treatment-emergent adverse events (TEAEs) are defined as AEs that started or worsened in severity on or after the first dose of study treatment.

Refer to Section 9.1.5 for handling of partial dates for AEs for the purpose of assigning treatment-emergent flags. In the case where it is not possible to define an AE as treatment-emergent or not, the AE will be classified as treatment-emergent.

Severity of TEAEs

Severity is classified as Grade 1: Mild, Grade 2: Moderate, Grade 3: Severe, Grade 4: Lifethreatening, Grade 5: Death related to AE, using the Common Terminology Criteria for Adverse Events, v5.0 (CTCAE v5.0).

Relationship of TEAEs to Study Treatment

Relationship is classified as "not related", "unlikely related", "probably related", or "related" by the Investigator.

TEAEs Leading to Discontinuation of Study Treatment

TEAEs leading to discontinuation of study treatment will be identified by action taken being recorded as "Drug withdrawal" on the Adverse Events electronic case report form (eCRF).

Serious and Non-Serious TEAEs

Serious adverse events (SAEs) are those events recorded as "Serious" on the Adverse Events eCRF.

TEAEs Leading to Death

TEAEs leading to Death are those events which are recorded with an outcome as "Fatal" on the Adverse Events eCRF.

TEAEs of Special Interest

Categories of Targeted Medical Events (TMEs) and a list of preferred terms associated with these TME categories were developed based on the mechanism of action of etrasimod, prior experience with other agents acting via a similar mechanism, and disease-specific clinical judgment. The proposed candidate terms will be reviewed along with other supportive data (eg, vital signs, lab) to identify which events reflect AESI.

Categories and subcategories of TEAEs of special interest are the following:

- Cardiovascular Events
 - Bradycardia
 - AV conduction delay
 - Hypertension
- Macular Edema
- Pulmonary Disorders
 - Airflow obstruction (forced expiratory volume in 1 second [FEV1], forced vital

- capacity [FVC])
- Decrease gas exchange (diffusing capacity of the lungs for carbon monoxide
- [DLCO]
- Infections
 - Severe infections
 - Opportunistic infections (Narrow)
 - Herpes simplex and herpes zoster
- Liver Injury
 - Liver transaminases elevation
 - Bilirubin elevation

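### SAP 6.3.1.1 and 6.3.1.5 define a related TEAE differently when causality is missing, so related-event counts will disagree if any TEAE lacks a causality entry

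*SAP*

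**What the plan says.** SAP 3.2.2.1 sets up causality with four investigator categories: "Relationship is classified as 'not related', 'unlikely related', 'probably related', or 'related' by the Investigator". It has no rule for a blank entry.

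SAP 6.3.1.1, under the heading on relationship to study treatment, plans a detailed table: "All related TEAEs will be summarized by SOC, PT, and maximum severity". It then states that a related TEAE "for the purpose of this summary is defined as a TEAE with relationship to study treatment of" probably related or related. Missing relationship is not mentioned.

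SAP 6.3.1.5 plans an overview that counts both participants and events. Its footnote says that the term "refers to TEAEs related or probably related to study treatment or are missing relationship". The asterisk is attached to five rows: any related TEAE, any related serious TEAE, related TEAEs leading to discontinuation, related TEAEs leading to interruption, and "Related TEAEs by maximum severity".

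**The concern.** The last starred overview row and the 6.3.1.1 table describe the same quantity, related TEAEs by maximum severity, at two levels of detail. A reader will expect the SOC/PT table to break down the overview count. Under the text as written, an event with blank causality counts as related in the overview and is left out of the related SOC/PT table.

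The direction is also unhelpful. The table that shows which related events occurred, and how severe they were, applies the narrower definition. For two other unknown AE classifications the SAP takes the cautious side. On seriousness, 6.3.1.3 says: "If the seriousness is missing, the AE will be considered as 'Serious' for summary tabulation purpose only". On timing, 3.2.2.1 classes an AE as treatment-emergent when that cannot be determined. At stake is the consistency and traceability of a reported safety count.

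**Working it through.** There is no planned figure to reproduce. The check is a comparison of text, followed by set arithmetic.

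**Side by side**

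| Recorded relationship | Related in the 6.3.1.1 table? | Related in the 6.3.1.5 starred rows? |
|---|---|---|
| Not related | No | No |
| Unlikely related | No | No |
| Probably related | Yes | Yes |
| Related | Yes | Yes |
| Missing | No | Yes |

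The definitions differ in one cell only. A rule elsewhere could have settled it, but none does. SAP 3.2.2.1 lists the four categories. SAP 6.3.1.3 deals with seriousness. SAP 9.1.5 deals with partial dates. The version history does not mention the difference.

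**Event counts.** Let *a* be the number of TEAEs recorded as related or probably related, and *m* the number with missing relationship.

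- Under 6.3.1.1: *a*
- Under 6.3.1.5: *a* + *m*
- Difference: (*a* + *m*) − *a* = *m*

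The difference cannot be negative. Whenever the two disagree, the 6.3.1.1 definition gives the lower count.

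**Participant counts.** The difference in participants with any related TEAE is the number who have at least one TEAE with missing causality and none recorded as related or probably related. It lies between 0 and the number of participants with any missing-causality TEAE. Three cases show the range:

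- *m* = 0: events differ by 0, participants by 0.
- *m* = 1, in a participant who also has a TEAE recorded as related: events differ by 1, participants by 0.
- *m* = 1, in a participant with no TEAE recorded as related or probably related: events differ by 1, participants by 1.

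In the second case the participant total agrees, but the severity split can still differ: if the missing-causality event is the more severe, the participant's maximum related severity is higher in the overview.

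**Which rows have a competing definition.** The other starred rows, on related serious events and related events leading to discontinuation or interruption, have no related-only SOC/PT table, because 6.3.1.2 and 6.3.1.3 tabulate such events whatever their causality. The direct clash is therefore in any related TEAE and in the maximum-severity row.

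**The case against.** The strongest reply is that nothing is ambiguous to program. The 6.3.1.1 definition is expressly limited to its own table, and 6.3.1.5 presents the overview as an addition to the earlier summaries. Each output has its own rule, and the difference could be deliberate. That stands as far as it goes. But the SAP gives no reason for the difference, and both outputs carry the same label.

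A second reply is that missing causality should be rare. Protocol 9.9.9.1.6 requires a documented causality assessment for each adverse event. For SAEs it adds that it is very important that "the Investigator always make an initial assessment of causality for every event" before the report is first sent. Protocol 9.9.9.2.2 lists relationship among the items to record on the AE eCRF. This is fair, and the discrepancy may turn out to be zero. The 6.3.1.5 footnote nevertheless provides for blanks.

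Three stronger readings are tempting, and the documents do not support them.

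- *The event drops out of the detailed reporting.* It does not. SAP 6.3.1.1 also tabulates all TEAEs by SOC, PT and maximum severity and lists every AE, so the event is still named and graded. It is absent only from the related subset.
- *The two tables cannot be reconciled.* The gap consists solely of events with missing relationship. The overview also has a row for TEAEs by relationship. If that row shows the four recorded categories by number of events, the remainder is *m*, and the listings allow the events to be traced.
- *6.3.1.1 breaks a general worst-case rule.* The SAP has no such rule for AE classifications. It has separate rules for particular fields, and consistency with them is a sound preference, not a provision that has been violated.

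**Conclusion.** The inconsistency is real and minor. One label has two counting rules that differ only for missing causality, and no other section reconciles them. The effect is conditional on at least one TEAE lacking a causality entry. The event counts then differ by the number of such events, and the participant totals by anything from zero upwards, as shown above. A reader might infer that the totals must differ, but the documents give no rate of missing causality and the protocol asks for it to be recorded, so that does not follow.

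No inference depends on this. The comparative analyses listed in SAP 6.3.1.5 contain no related-TEAE item, and efficacy, alpha and power are unaffected. It is worth correcting because the correction is easy and moves a reported safety count in the conservative direction.

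**What to change.** In SAP 6.3.1.1, define a related TEAE as one that is probably related, related, or missing relationship. Leave 6.3.1.5 as it is. Both outputs then follow one rule, in line with the SAP's handling of missing seriousness and unclear treatment emergence.

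The cost is a few words in the SAP and the matching selection condition for one table. The downside is that related counts in the SOC/PT table may be slightly higher; if no causality entry is missing, no number changes. If the sponsor does want two definitions, the second-best course is to label the two outputs differently and state the reason.

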10.2. Determination of Sample Size

Based on a 2-group Fisher's exact test, a two-sided significance level of 0.05, and a 2:1 randomization ratio, approximately 183 subjects (122 etrasimod, 61 placebo) are required to achieve at least 80% power to detect a difference of 20% in the primary endpoint of clinical remission (based on MMS) at Week 52 between the etrasimod treatment group (34%) and the placebo treatment group (14%). Alternatively, based on the same assumptions, using normal approximation to the binomial distribution, a two-sided test would achieve at least 90% power. The assumptions are based on the final analysis results in the Phase 3 Studies APD334-301 and APD334-302. Sample size is calculated using the EAST® software.

At the time of this amendment, approximately 45 subjects among the already randomized subjects (assuming approximately 2:1 ratio of etrasimod placebo) do not meet the amended Inclusion Criterion 5 in Study APD334-210 protocol amendment 2.0, which includes ES score ≥ 2 and RB score ≥ 1. As a result, these subjects will be excluded from the Primary Analysis Set (refer to section 10.3) but these subjects will be included in other analysis sets as deemed appropriate. Therefore, approximately 225 total subjects (150 etrasimod, 75 placebo) are required to be enrolled into study.

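### The planned large-sample Poisson interval for exposure-adjusted rate differences has no sparse-count rule: it is exactly [0, 0] when both arms are empty and too narrow when one arm is empty

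*SAP*

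**What the plan says.** SAP 6.3.1.5 lists the adverse event groups to be compared between arms. They include "TEAEs leading to Deaths", opportunistic infections (narrow definition) and "Treatment-emergent Malignancies", and also groups that need not be rare, such as severe and serious events and discontinuations.

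Each group gets two intervals. The first is on the risk scale: "Risk differences between etrasimod and placebo along with 95% CIs using the Wilson's score method will be presented". The second is on the EAIR scale, with "95% CIs based on large-sample approximation assuming Poisson standard errors for the estimated incidence rates", citing a methods paper.

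SAP 6.3.1.1 defines the rate: "The EAIR is calculated as the number of participants with the AE divided by the total exposure in participant-years". Exposure runs to the first event, or is "time (year) from first dose to last participation for those who did not experience this AE".

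The section gives no minimum event count, no exact or score fallback for the rate difference, and no instruction for an empty arm. On size, Protocol 10.2 says "approximately 225 total subjects (150 etrasimod, 75 placebo) are required to be enrolled into study".

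**The concern.** A large-sample interval estimates its standard error from the observed counts. When a count is zero, the estimated variance for that arm is zero as well, although the uncertainty is not. Several groups in the list are ones where no events in about 75 placebo participants would be unsurprising. Protocol 3.2 reports no deaths in the earlier Phase 2 study.

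Readers use these intervals to judge how large an excess of a rare harm the trial leaves open. An interval that is too short can suggest that an excess has been ruled out when it has not, or can flag a difference on very few events.

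**Working it through.** **Inputs.** The documents give arm sizes of about 150 and 75 but no participant-years. The arm sizes are consistent with the plan's own figures: exact enumeration of Fisher's test at 122/61 with 34% v 14% gives 83.8% power (stated: at least 80%), and 183 + 45 = 228 against the stated approximate 225. With up to 52 weeks of treatment I assume 150/75 PY, with a range from 105/45 (early exits) to 162/81 (including the 4-week follow-up). The plan states no figure for the EAIR interval itself.

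**Planned interval.** With x1, x0 events and T1, T0 PY:

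(x1/T1 − x0/T0) ± 1.96 × √(x1/T1² + x0/T0²)

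- 0 v 0: 0 ± 0, so [0, 0].
- 1 v 0: 1/150 = 0.667 per 100 PY, SE 0.667, so 0.667 ± 1.307 = -0.64 to 1.97.
- 4 v 0: 4/150 = 2.667, SE 2/150 = 1.333, so 2.667 ± 2.613 = 0.05 to 5.28.

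With an empty placebo arm the lower limit is (x1 − 1.96√x1)/T1. It is positive once x1 exceeds 1.96² = 3.84, so 4 v 0 excludes zero at any exposure.

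**Comparators.** The score interval uses the variance at the restricted maximum likelihood estimate (Miettinen-Nurminen type). At 0 v 0 its limits are −1.96²/T0 and 1.96²/T1, that is −3.84/75 = −5.12 and 3.84/150 = 2.56 per 100 PY. The hybrid interval combines exact Poisson limits for each arm. At 0 v 0 its upper limit is −ln(0.025)/150 = 3.689/150 = 2.46.

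Per 100 PY at 150/75 PY:

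| Etrasimod v placebo events | Planned (Wald) | Score | Hybrid exact | Wald width / score width |
|---|---|---|---|---|
| 0 v 0 | 0.00 to 0.00 | -5.12 to 2.56 | -4.92 to 2.46 | 0 |
| 1 v 0 | -0.64 to 1.97 | -4.46 to 3.78 | -4.29 to 3.71 | 0.32 |
| 2 v 0 | -0.51 to 3.18 | -3.79 to 4.86 | -3.72 to 4.82 | 0.43 |
| 3 v 0 | -0.26 to 4.26 | -3.12 to 5.88 | -3.17 to 5.84 | 0.50 |
| 4 v 0 | 0.05 to 5.28 | -2.46 to 6.86 | -2.62 to 6.83 | 0.56 |
| 0 v 1 | -3.95 to 1.28 | -7.55 to 1.23 | -7.43 to 1.45 | 0.60 |
| 0 v 2 | -6.36 to 1.03 | -9.72 to -0.11 | -9.63 to 0.73 | 0.77 |

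Over the exposure range, the score upper limit at 0 v 0 runs from 3.84/162 = 2.37 to 3.84/105 = 3.66. If the rates are equal, all four of four events fall on etrasimod with probability (2/3)⁴ = 0.198, so the Wald exclusion of zero at 4 v 0 is not evidence of a difference.

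**How likely are empty arms?** At a true rate of 0.5 per 100 PY in both arms, the placebo arm is empty with probability exp(−0.005 × 75) = 0.69, and both arms with probability exp(−0.005 × 225) = 0.32. At 105/45 PY these become 0.80 and 0.47.

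**Coverage of the planned interval** (enumeration of independent Poisson counts):

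- *Etrasimod rate higher*, 1.0 v 0.3 per 100 PY: 82% at 150/75 PY and 77% at 130/60 PY. The probability of 0 v 0 is exp(−1.725) = 17.8% and exp(−1.48) = 22.8% respectively, which is almost the whole miss.
- *Placebo rate higher*, at 130/60 PY: 60% for 0.3 v 1.0, 70% for 1.0 v 2.0 and 70% for 0.5 v 2.0. The misses are at the lower (benefit-side) limit: 40.4%, 30.1% and 30.1%. The upper (harm-side) limit misses at most 0.3%.
- *Equal rates*, 0.5 to 5 per 100 PY at 150/75 and 105/45 PY: 91% to 99.8%.

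The score interval covers 93% to 99.6% at the four unequal-rate pairs at 130/60 PY.

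**The case against.** The strongest answer is that the same paragraph also plans Wilson score risk differences for every listed event. Over about one year, risk per 100 participants and rate per 100 PY are close in scale. Reading the method as the Newcombe hybrid, the risk difference is -4.87 to 2.50 points at 0 v 0, -4.24 to 3.68 at 1 v 0 and -2.47 to 6.66 at 4 v 0. That stands, so the planned safety output as a whole does contain honest intervals. It does not repair the EAIR column: at 4 v 0 one interval includes zero and the other excludes it, and the SAP does not say which to rely on.

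A reader might infer that the interval collapses whenever one arm is empty, that all the rare-harm intervals are affected, or that the trial will generally seem to rule out excess harm. The documents do not support these readings. Zero width needs both arms empty. The Wilson column is sound. When placebo has the higher rate, the misses understate possible benefit and do not exclude harm.

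Nor does 6.3.1.5 clearly extend the EAIR comparison to each preferred term of special interest; comparisons at that level are assigned to the Cox model in 6.3.1.4.

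Replacing Wald with a score interval for every event is not a clean remedy either. The score interval excludes zero at 0 v 2, and its harm-side limit is slightly tighter than Wald's at 0 v 1 (1.23 v 1.28 at 150/75 PY) and at 10 v 5 (7.46 v 8.08 at 130/60 PY).

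**Conclusion.** The concern holds for the EAIR differences when counts are sparse. At 0 v 0 the planned interval has no width, where a score interval leaves open an excess of 2.4 to 3.7 per 100 PY over the exposure range. With 1 to 4 etrasimod events and none on placebo, it has 32% to 56% of the score width at 150/75 PY. The consequence can go either way: false reassurance at 0 v 0, or a spurious signal at 4 v 0.

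This is descriptive safety output. The primary analysis and its type I error are unaffected, and the interval is reasonable for common events.

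The figures rest on assumed participant-years and Poisson counts. The SAP wording is taken at face value: the cited methods paper was not available, so any sparse-count handling it contains could not be checked. If the sponsor intends such handling, the SAP should say so.

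**What to change.** In SAP 6.3.1.5, add a sparse-count rule for the EAIR difference. When either arm has few events (for example fewer than 5), replace the large-sample interval with one of these:

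- an exact-based interval, for example the hybrid built from exact Poisson limits, which includes zero at 0 v 2 (-9.63 to 0.73); or
- a score interval, with a note that it can exclude zero at 0 v 2.

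Print no Wald interval at 0 v 0, and keep the large-sample interval for common events.

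The cost is one SAP sentence and a small macro. Sparse-event intervals become wider overall, although the score version's harm-side limit is not wider in every case.
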